Medical assessments include a complete neurologic examination including documentation of cranial nerve, motor, sensory, cerebellar, and deep tendon reflex examinations; interim history (since last visit); vital signs; physical examination (at baseline); targeted physical exam (Day 0-28, End of Radiation +2-+110 weeks, and Post-treatment follow up visits) and ECOG performance status. To be performed within 3 days prior of each dose of vaccine. Repeat medical assessment is not required at baseline if history and physical has been performed within 3 days of vaccine administration on day 0.

Serum HIV antibody should be completed within 6 months of initiating treatment.

Serum hepatitis B & C antibody should be completed within 6 months of initiating treatment.

Chemistry panel: Na+, K+, Cl, CO2, glucose, (BUN), creatinine, albumin, alkaline phosphatase, ALT, AST, total bilirubin, thyroid stimulating hormone (TSH), calcium, and ANA to be performed within 16 days prior to screening/ baseline per protocol. TSH is optional after screening visit.

In females of child-bearing potential, Beta-HCG to be done at baseline 48 hours prior to treatment and within 48 hours of any dose of vaccine or radiation.

CT chest, abdomen, and pelvis and MRI (if target lesion is best visualized by MRI)

Correlative biomarker studies (blood): 6 (10 mL) green top sodium heparin tubes for PBMC; 1 (8.5 mL) SST tubes for serum samples.

Radiotherapy schedule and dose selected by treating radiation oncologist. Radiotherapy will begin at least 2 weeks and ideally not more than 4 weeks after first administration of FPV-Brachyury (Dose 3).

 RECIST based assessment includes using RECIST principles (see [Section 10.5](#)) to measure the “target” lesions, defined as those meeting RECIST requirements for measurability and those that will be treated with radiation as defined by minimum requirements of the protocol. “Non-target” lesions may include those that are not measurable by RECIST or those that are measurable and not treated with radiotherapy at the dose required by protocol (per [Section 6.3.1](#)).

Time noted is from end of radiation or until resolution of AEs related to radiation, whichever is later

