### 4.2.2.2 Evaluation of Response

Appropriate imaging with CT of the chest/abdomen/pelvis and MRI (if target lesion is best visualized by MRI) to reassess tumor extent and to determine tumor measurements will be performed 14 weeks after completion of radiotherapy and with each subsequent dose of vaccine thereafter (with windows for treatment as designated in the schedule of events, [Section 1.5](#)).

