##### **6.3.1.1 Minimum Radiation Treatment Requirements**

1. The minimum radiotherapy dose required for biologic effect is established based on the preclinical data as 8 Gy in 1 fraction. The following are examples of calculations that are equivalent doses biologically to 8 Gy in 1 fraction. For each patient, the treating radiologist should calculate the biologic equivalent dose to ensure that the minimum biologic dose is reached. Any dose at least meeting this equivalence is potentially eligible, given that the treating radiation oncologist does not believe the dose will cause harm to normal surrounding structures.
  - a. 8 Gy in 1 fraction (8 Gy / fraction)
  - b. 20 Gy in 5 fractions (4 Gy per fractions; minimally 12 Gy received)
  - c. 30 Gy in 10 fractions (3 Gy/fraction; minimally 15 Gy received)
  - d. 40 Gy in 20 fractions (2 Gy / fraction; minimally 20 Gy received)
2. Normal tissue surrounding the tumor must be protected by the standards of the treating institution for that organ system. For example, if a given institution requires that no normal spinal cord tissue receives more than a maximum point dose of 30 Gy (using 6 Gy / fraction bioequivalence), the treating radiation oncologist must comply with institutional standards when calculating the dose to the tumor center. This capability to meet requirements 1 and 2 must be determined for the target lesion prior to enrollment on trial.

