### **6.3.1.2 Guidelines for Radiotherapy for Definitive/Unresected Chordoma Treated with Curative Intent:**

To allow for standardization of radiation treatments, the following recommendations are provided:

For treatment of unresected primary or recurrent chordomas with gross measurable disease, the following treatment is recommended based on a series of experience ([DeLaney et al., 2009](#)) ([Park et al., 2006](#)) ([Chen et al., 2013](#)) ([Kabolizadeh et al., 2017](#)) showing high local control with these treatment volumes and doses.

**Gross Target Volume (GTV):** The GTV is any gross tumor(s) visualized on the treatment planning CT scan and or MRI.

**CTV1 (Clinical Target Volume 1)** is the GTV and tumor bed plus all tissues suspected on invasion by tumor on a subclinical basis. This includes 1.5 to 3 cm margin for areas of extraosseous extension into muscular compartments such as gluteus muscles, piriformis muscles, erector spinae muscles or along neurovascular bundles such as sciatic nerve; the entire involved vertebra; a vertebral level above and below the maximal extent of intraspinal canal involvement; and 0.5-1.0 cm in bone or abutting soft tissue confined by a fascial, cartilaginous, bone, or disc space barrier, bowel, lung interface. Generally the CTV1 dose level should be reduced to 45 to 46.80 GyRBE (gray relative biological effectiveness) in patients with these co-morbidities: active autoimmune disease, insulin requiring diabetes.

CTV1 will receive a dose of 50.4 Gy (or GyE with Relative Biological Effectiveness of 1.1 to 1 proton: photons if given with protons)

CTV2 will consist of the GTV plus any tumor bed with a 0.5 cm margin and should receive an additional dose of up to 27 Gy in 1.8 Gy per fraction or equivalent.

**Planned Target Value (PTV):** The clinical target volumes will be expanded (generally by 2-5 mm based on institutional practices) to generate a PTV to account for the intrafraction motion anticipated for the target volume in the immobilized patient during the treatment delivery. The prescribed dose is specified to the isodose contour which encompasses the planning target volumes on each proton field; this must be >95%.

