Modified Response Evaluation Criteria in Solid Tumors (mRECIST): Standard Response Evaluation Criteria in Solid Tumors (RECIST) Version 1.1 to be used only for radiographic assessment of the irradiated tumor(s) (target lesions). Non-irradiated tumors (non-target lesions) will not be part of the mRECIST assessment. Refer to Section 3.5.3.2 for additional details.

**Response:** Response for the primary analysis will be determined using mRECIST or Immune-Related Response Criteria (irRC), in which only target tumors receiving adequate radiotherapy will be considered for RECIST assessment and primary endpoint analysis. Progression of non-

BRACHY-CHOR-001

target lesions will be assessed as exploratory analyses based on standard RECIST 1.1 for this trial. Refer to Section 3.5.3.2 for additional details.

**Progressive Disease (PD)**: Advancement of disease as defined by target tumor enlargement from nadir using mRECIST or irRC. Progression of non-target lesions will not be considered as disease progression for the primary endpoint analysis of this trial.

**Target Lesions:** Only tumors that are measurable and have received adequate radiotherapy will be considered target lesions for determination of response. All other tumors will be considered non-target lesions.

**Objective Response (OR)**: A subject achieving Complete Response (CR) or Partial Response (PR) per mRECIST or irRC.

Objective Response Rate (ORR): The proportion of subjects meeting the criteria for OR.

**Duration of Response**: From the time that criteria are first met for CR or PR (whichever is first recorded) until the first date that recurrent or progressive disease is objectively documented. The smallest target-tumor measurements on trial (i.e., nadir tumor load) will be used as reference for progressive disease.

**Progression Free Survival (PFS)**: The time interval from the date of first trial vaccination to objective tumor progression, or death from any cause occurring prior to tumor progression. The rate of PFS at a fixed time point is defined as the proportion of subjects who have not experienced objective progression or death from the date of first trial vaccination to the fixed time point of interest.

**Brief Pain Inventory-Short Form (BPI-SF)**: A questionnaire to evaluate the severity of a subject's pain and the impact of this pain on the subject's daily functioning.

02 November, 2021

BRACHY-CHOR-001

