**BRACHY-CHOR-001** 

- Completed radiation therapy, and
- At least 3 out of 4 booster doses of FPV-Brachyury in 14 weeks after radiation, and
- Have both baseline (defined as measurement prior to first prime dose of MVA-BN-Brachyury), and at least one post-baseline computed tomography (CT) or magnetic resonance imaging (MRI) scan for objective tumor evaluation.

The primary analysis population for ORR anytime within 12 months after completion of radiation and secondary efficacy endpoints is the EAS. Subjects who failed to meet the evaluable criteria will be replaced to retain the statistical power unless four or more responses have been observed or the number of responders will still be less than four even if all replacement subjects would be responders. If there are more than 10 evaluable subjects at the end of stage 1 analysis or more than 29 evaluable subjects at the end of stage 2 analysis, primary evaluation will be based on the first 10 accrued or first 29 accrued evaluable subjects. Sensitivity analyses will include all evaluable subjects if applicable.

The FAS consists of all subjects who have enrolled and received any dose of MVA-BN-Brachyury or FPV-Brachyury. This is the primary analysis set for safety and immune response, and the secondary analysis set for efficacy.

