## 3.5.3.4 Secondary Efficacy Analyses

## 3.5.3.4.1 PFS Based on Target Lesion(s)

PFS is defined as the time interval from first vaccination to objective tumor progression based on the mRECIST criteria or death, whichever occurs first. Subjects who do not have disease progression or have not died will be censored at the date when the last tumor assessment determines a lack of target tumor progression. The product-limit Kaplan-Meier curve will summarize PFS graphically. Median survival and 95% confidence intervals will be computed based on the product limit method (Greenwood's formula for the standard error estimate) overall and by subgroups defined in Section 3.3. Progression-free survival rates will be summarized by visit where scheduled tumor assessment is performed, along with their Wilson score confidence intervals.

Primary analyses of PFS will be based on the EAS. PFS rates will also be summarized for the FAS where subjects without post-treatment tumor assessment will be considered to have progressed. Median survival and 95% confidence interval will not be analyzed for the FAS, as these estimates will not differ from those for the EAS because censoring at time 0 is equivalent to excluding these subjects.

Additionally, PFS from current treatment versus PFS from previous treatment will be explored. The ratio of current treatment PFS in days / previous treatment PFS in days for each subject will be calculated. Summary statistics will be presented for EAS. It will also be summarized for EAS by current radiation treatment dose categories: <= median current radiation dose in Gray and > median current radiation dose in Gray. Highest dose of radiation treatment for each subject is used as defining the current radiation treatment dose categories. Subject's most recent previous treatment will be used for the derivation and calculation of PFS from previous treatment. Figures will also be generated to present the ratio by overall and by current treatment radiation dose categories.

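### The dose split of the exploratory PFS ratio tends to favor longer radiotherapy courses, because current PFS counts from first vaccination while scans are timed from end of radiotherapy

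*SAP*

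**What the plan says.** SAP 3.5.3.4.1 sets out the ratio: "The ratio of current treatment PFS in days / previous treatment PFS in days for each subject will be calculated". Previous PFS comes from the most recent previous treatment. The ratio is summarized in the evaluable analysis set (EAS), overall and by dose: "It will also be summarized for EAS by current radiation treatment dose categories". The cut is at the median in Gray, using each subject's highest dose. Figures follow the same split.

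The clock for current PFS is given in the SAP General Definitions: "The time interval from the date of first trial vaccination to objective tumor progression, or death from any cause occurring prior to tumor progression". Section 3.5.3.4.1 sets no other start for the ratio.

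Imaging runs on a different clock. Under Protocol 4.2.2.2, scans "will be performed 14 weeks after completion of radiotherapy and with each subsequent dose of vaccine thereafter". The schedule in Protocol 1.5 has no scan between baseline and that visit, and footnote 11 can push the visits later: "Time noted is from end of radiation or until resolution of AEs related to radiation, whichever is later".

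EAS membership (SAP 3.2) requires both prime doses, one booster before radiation, completed radiotherapy, "At least 3 out of 4 booster doses of FPV-Brachyury in 14 weeks after radiation, and" a baseline scan with at least one later scan. It does not require the subject to be progression-free at any point.

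Dose and course length rise together in the fractionated regimens that the protocol lists. Section 6.3.1.1 runs from 8 Gy in 1 fraction to "40 Gy in 20 fractions (2 Gy / fraction; minimally 20 Gy received"). Section 6.3.1.2 recommends 50.4 Gy to the first clinical target volume, and the second "should receive an additional dose of up to 27 Gy in 1.8 Gy per fraction or equivalent".

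**The concern.** Unless an unscheduled scan is done, an EAS subject's target-lesion progression cannot be dated before the first scan after radiotherapy. The days up to the end of radiotherapy are then counted as progression-free, and course length decides how many there are. The denominator comes from an earlier treatment and cannot offset this. Dose in Gray, the splitting variable, partly stands in for course length, so a higher ratio above the median dose could be read as a dose effect when part of it is radiotherapy calendar time.

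The stakes are limited. The ratio is exploratory, with no test or threshold. The response rate, the two-stage decision rule, EAS membership and the by-visit PFS rates do not depend on it.

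**Working it through.** The plan states no figure for this ratio, so there is nothing to reproduce first.

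**Inputs from the documents.** Dose 3 is on Day 28 and radiotherapy starts 2 to 4 weeks later, so on Day 42 to 56 (Protocol 4.2). Scans come 14 weeks after radiotherapy and then every 12 weeks to week 110 (Protocol 1.5, 4.2.2.2). The regimens are those of Protocol 6.3.1.1 and 6.3.1.2.

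**Assumptions.** Five fractions per week with a Monday start; 1.8 Gy per fraction throughout the definitive course. Then 50.4/1.8 = 28 and 27/1.8 = 15, so 77.4 Gy takes 43 fractions. A smaller boost to 70.2 Gy takes 70.2/1.8 = 39.

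**Step 1: day of the first scheduled scan** = 42 + days from first to last fraction + 98.

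| Course | Course days | First scan |
|---|---|---|
| 8 Gy / 1 | 0 | Day 140 |
| 20 Gy / 5 | 4 | Day 144 |
| 30 Gy / 10 | 11 | Day 151 |
| 40 Gy / 20 | 25 | Day 165 |
| 70.2 Gy / 39 | 52 | Day 192 |
| 77.4 Gy / 43 | 58 | Day 198 |

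A Day 56 start adds 14 days to each.

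**Step 2: same result at the same visit, equal previous PFS.** For 43 against 1 fraction the numerators stand as 198/140 = 1.41 at week 14, 282/224 = 1.26 at week 26, 450/392 = 1.15 at week 50 and 870/812 = 1.07 at week 110. For 43 against 20 fractions they are 198/165 = 1.20, 282/249 = 1.13, 450/417 = 1.08 and 870/837 = 1.04.

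**Step 3: mean difference in the numerator with no dose effect.** This was simulated with exponential time to target progression, recorded at the next scheduled scan, and a Day 42 start. Subjects still progression-free at week 110 were given that day, because the SAP has no rule for a censored numerator. The share progressed by Day 140 is an assumed range. Counting from end of radiotherapy subtracts 58 days (43 versus 1) or 58 − 25 = 33 days (43 versus 20).

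| Progression risk counted from | 43 v 1, planned clock | 43 v 1, end-of-radiotherapy clock | 43 v 20, planned clock | 43 v 20, end-of-radiotherapy clock |
|---|---|---|---|---|
| End of radiotherapy | +58.0 | 0 | +33 | 0 |
| First vaccination, 5% by Day 140 | +45.9 | −12.1 | +26.1 | −6.9 |
| First vaccination, 10% | +37.1 | −20.9 | +21.2 | −11.8 |
| First vaccination, 20% | +26.9 | −31.1 | +15.7 | −17.3 |
| First vaccination, 33% | +23.6 | −34.4 | +14.1 | −18.9 |

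The planned clock errs upward for the longer course in every row. The other clock errs at or below zero. If previous PFS is independent of course length, the mean ratio moves in the same proportion as the mean numerator.

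**Step 4: the median.** When risk counts from first vaccination, the median moves in scan steps. At 33% progressed by Day 140 it is 308 days after 1 fraction and 282 after 43, so the longer course is lower.

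**Step 5: similar courses.** For 70.2 against 77.4 Gy the calendar difference is 58 − 52 = 6 days. A run with median PFS of 9 months and start dates spread over Day 42 to 56 gave 538.6 − 531.3 = 7.3 days among subjects progression-free 10 weeks after radiotherapy. Without that restriction it gave 417.5 − 415.4 = 2.1 days.

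**Step 6: the overall ratio.** Take a previous PFS of 120 days and target progression on Day 60 that no unscheduled scan picks up. The recorded ratio is 140/120 = 1.17 after one fraction and 198/120 = 1.65 after 43, although the exact-date ratio is 60/120 = 0.50.

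**The case against.** The strongest objection is to the obvious remedy of simply restarting the clock at end of radiotherapy. The EAS does not exclude undetected early progressors: they go on receiving boosters until the first scan. If risk runs from first vaccination, the new clock reverses the bias, and for 43 versus 1 fraction at 20% and 33% the error is larger than under the planned clock (−31.1 against +26.9, −34.4 against +23.6). It also puts numerator and denominator on different starts, so the value 1 loses its meaning. This stands, and it rules out replacing the clock.

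A reader might infer that higher doses score higher by construction, or by some 41%. The documents do not support that. The 41% pairs the shortest listed course with the longest, both progressing at the first scan, whereas Protocol 2.5.10 expects most doses to exceed the minimum. Stereotactic body radiotherapy (Protocol, Quality Assurance) and radiosurgery (SAP 3.5.7) can give a high dose in few fractions. Classifying by highest dose loosens the link further in subjects with several treated lesions.

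Noise is also large. With 15 versus 14 subjects, median PFS of 9 months and no dose effect, 43 versus 1 fraction shifts the mean ratio by 0.12 to 0.27 against a sampling SD of about 0.8. The longer-course group then looks better in 56% to 63% of trials, against 50% by chance. This limits how often the artefact would mislead but does not remove it.

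Finally, SAP 3.5.3.3.1 already plots lesion change by dose group at each visit, which avoids the clock problem, and SAP 3.5.7 reports dose and fractions. Neither tells the reader of the ratio table how much of a difference is course length.

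**Conclusion.** The concern holds as a tendency in the mean, in an exploratory output. Where higher dose goes with a longer course, the planned ratio mixes course length with tumor control. With no dose effect, the mean numerator is longer by about 24 to 58 days for 43 versus 1 fraction, about 14 to 33 days for 43 versus 20, and at most about 6 to 7 days for 70.2 versus 77.4 Gy. The position within each range depends on when progression risk starts and how many early progressors stay in the EAS. The figures assume five fractions per week, exponential progression times and nominal visits; footnote 11 delays are left out. The documents do not give the dose mix, so the size in this trial cannot be fixed in advance.

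Two further readings do not follow. The by-visit PFS rates are proportions at each subject's own post-radiation visit and need no change. No choice of clock makes the dose groups comparable, because definitive and palliative courses differ in treatment intent (Protocol 6.3.1.2 and Quality Assurance). The point is a worthwhile small improvement.

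**What to change.** In SAP 3.5.3.4.1, for the dose-category summary and figures:

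- Keep the planned ratio from first vaccination. Beside it, show a version with current PFS counted from the last day of radiotherapy, and report radiotherapy course length by dose group.
- State that the first version tends to favor longer courses, and that the second can favor shorter ones if target lesions progress undetected before or during radiotherapy. State that a dose pattern is described only if both versions agree, and that the second version is not read against 1.

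For the overall ratio, report how many subjects had a previous PFS shorter than the day of their own first post-radiation scan. Unless an unscheduled scan comes first, their ratio exceeds 1 whatever the target lesion does before that scan.

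The cost is one derived variable, one extra column and one count in an exploratory table. The dose and schedule of radiotherapy are already documented (Protocol 4.2), and the SAP already lists the last day relative to radiotherapy (3.5.4). No new data are needed and the primary analysis is unchanged.

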The selection of the minimum allowable dose of radiation is based on the preclinical *in vitro* work where 8Gy of radiation was applied to the chordoma cells ([Gameiro et al., 2016](#)). It is likely that, in most cases, a higher dose of radiotherapy may be used clinically, but a minimum threshold of biologic effect is set based on the preclinical work. In this clinical trial, the dose of radiation will be determined, in each case, by the treating radiation oncologist as per standard treatment guidelines.

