#### **6.3.1 Radiotherapy**

Radiotherapy must meet minimum requirements to achieve a reasonably effective dose. The minimum expected dose to provide biologic rationale for the combination is 8Gy in 1 fraction for each target lesion. Documentation by a radiation oncologist of an equivalent or higher biologic dose is adequate to meet requirements for eligibility and treatment on protocol. A patient who does not cross this threshold is not considered to have received treatment per protocol and will not be assessed for response per RECIST 1.1 criteria for the primary analysis/objective.

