## Quality Assurance

### Dose Specification

A minimal of 95% of the prescription dose should be prescribed to a minimum of 95% of target volume at each dose level. Deviations and reasons for deviation should be recorded.

Radiation guidelines for treatment of metastases or recurrences with palliative intent: Palliative radiation given to metastases or recurrences at primary site may vary across institution. Details of dose, fractionation, and technique should be recorded. A minimum of 8 Gy x 1 (or biologic equivalent as described in [Section 6.3.1.1](#)) should be used for palliation. Stereotactic body radiotherapy (SBRT) should follow standard guidelines for safety.

Radiation to secondary non-target sites: May be allowed if demonstrates progression and will be evaluated for RECIST 1.1 response.

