**BRACHY-CHOR-001** 

The 90% Wilson score confidence intervals will be calculated. The duration of response and tumor measurements will only be provided in subject-level listings.

Percent change from Baseline in target lesion by visits will be plotted for the EAS by different subgroups: best OR, current radiation dose group categories (≤ median current radiation dose in Gray and > median current radiation dose in Gray), baseline disease location, and therapy type (proton therapy and other therapy).

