## 3.5.7 Treatment Exposure and Compliance

MVA-BN-Brachyury will be given subcutaneously (SC) for one dose each on Day 0 and Day 14. One dose = four 0.5 mL injections for a total dose of at least  $5 \times 10^7 \text{ Inf.U}$ .

FPV-Brachyury will be given SC on Day 28 visit, then every 4 weeks for 4 doses (End of Radiation + 2, 6, 10, and 14 weeks), then given every 12 weeks (End of Radiation + 26, 38, 50, 62, 74, 86, 98, and 110 weeks). One dose = one 0.5 mL injection with a nominal titer of 1 x  $10^9$  Inf.U per 0.5 mL.

All summaries of treatment exposure will be based on the FAS. The total number of MVA-BN-Brachyury injections will be summarized categorically as 0 - < 4, 4 - < 8, 8, and > 8. The total number of FPV-Brachyury doses will be summarized numerically and categorically as 0 - < 4, 4 - < 8, 8 - 12, and > 12. Total duration of exposure in weeks is defined as (date of last trial vaccination - date of first trial vaccination + 1) / 7. Duration of exposure will be summarized descriptively.

For radiation therapy, the percentage of subjects with different numbers of target lesions treated and non-target lesions treated (e.g., 1, 2, 3, 4 etc.) will be summarized separately. Summaries for radiation type (external beam, intensity-modulated radiation therapy [IMRT], photon beam, proton beam, stereotactic radiosurgery [SRS]), total radiation dose (Gy), and total number of fractions delivered will be summarized based on N = total number of target lesions treated or N = total number of non-target lesions treated.

All exposure data will also be provided in subject-level listings.

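### The exploratory radiation dose groups are cut at the median dose in Gray, which ignores fraction size; a version by biologically effective dose would be a cheap optional addition

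*SAP*

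**What the plan says.** SAP 3.5.3.3.1 plots percent change in the target lesion by several groupings, among them "current radiation dose group categories (≤ median current radiation dose in Gray and > median current radiation dose in Gray". SAP 3.5.3.4.1 summarizes the ratio of current to previous PFS by "current radiation treatment dose categories: <= median current radiation dose in Gray and > median current radiation dose in Gray", and adds: "Highest dose of radiation treatment for each subject is used as defining the current radiation treatment dose categories". Neither section mentions number of fractions, dose per fraction, BED or EQD2 (the equivalent dose in 2 Gy fractions).

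The protocol uses a biologic scale for its minimum dose. Section 6.3.1 states: "Documentation by a radiation oncologist of an equivalent or higher biologic dose is adequate to meet requirements for eligibility and treatment on protocol". Section 6.3.1.1 introduces its list of schedules with: "The following are examples of calculations that are equivalent doses biologically to 8 Gy in 1 fraction". Above that minimum the choice is individual. Protocol 2.5.10 says that "the dose of radiation will be determined, in each case, by the treating radiation oncologist as per standard treatment guidelines". The palliative guidance under Dose Specification adds: "Stereotactic body radiotherapy (SBRT) should follow standard guidelines for safety". SAP 3.5.7 lists stereotactic radiosurgery (SRS) among the radiation types, and says that "total radiation dose (Gy), and total number of fractions delivered will be summarized" by treated lesion.

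**The concern.** The same total dose has a larger biologic effect when it is given in fewer, larger fractions. A stereotactic or other hypofractionated course can therefore have a low total in Gray and still be as intense as a long conventional course with a much higher total. A cut at the median Gray would put such a patient in the lower group, beside patients given low-dose palliation.

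The trial has a single arm, and radiation intensity is an obvious alternative explanation for shrinkage of an irradiated lesion. These two sets of displays are the only planned efficacy displays by radiation dose. If their lower group mixed low and high intensities, they could not be read as a comparison by intensity.

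**Working it through.** **Formula and assumptions.** BED = D × (1 + (D/n)/(α/β)), where D is total dose and n the number of fractions. The linear-quadratic model and α/β are assumptions, since the documents give neither. The working range for α/β is 2 to 10.

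**1. The protocol's own equivalence.** Section 6.3.1.1 gives 8 Gy in one fraction, and minimum received doses of 12 Gy at 4 Gy per fraction, 15 Gy at 3 Gy and 20 Gy at 2 Gy. In that order the BEDs are:

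- α/β 2: 40, 36, 37.5, 40
- α/β 3: 29.3, 28, 30, 33.3
- α/β 10: 14.4, 16.8, 19.5, 24

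Total Gray differs 2.5-fold (20/8). BED is nearly constant at the lower α/β values and less so at 10. The formula therefore broadly reproduces the protocol's equivalence.

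**2. Does Gray misrank the full courses that the documents name?** The inputs are the four full schedules in 6.3.1.1, and from 6.3.1.2 the doses 45, 46.8 and 50.4 Gy and 50.4 + 27 = 77.4 Gy. The protocol states 1.8 Gy per fraction only for the boost; it is assumed here for all four 6.3.1.2 doses.

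| Course (Gy/fractions) | BED, α/β 2 | α/β 4 | α/β 10 |
|---|---|---|---|
| 8/1 | 40 | 24 | 14.4 |
| 20/5 | 60 | 40 | 28 |
| 30/10 | 75 | 52.5 | 39 |
| 40/20 | 80 | 60 | 48 |
| 45/25 | 85.5 | 65.2 | 53.1 |
| 46.8/26 | 88.9 | 67.9 | 55.2 |
| 50.4/28 | 95.8 | 73.1 | 59.5 |
| 77.4/43 | 147.1 | 112.2 | 91.3 |

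The order by BED equals the order by Gray. This also holds at every other α/β tried from 1 to 20, with one tie (30/10 and 40/20, at α/β 1).

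**3. Which courses would change the ranking?** As reference take the middle of the recommended range, (50.4 + 77.4)/2 = 63.9 Gy, at 1.8 Gy per fraction. Its BED is 63.9 × (1 + 1.8/2) = 121.4 at α/β 2, and 63.9 × (1 + 1.8/10) = 75.4 at α/β 10. The total dose in n fractions with equal BED is D = [−n·α/β + √((n·α/β)² + 4·n·α/β·BED)]/2:

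| Fractions | α/β 2 | α/β 10 |
|---|---|---|
| 1 | 14.6 Gy | 22.9 Gy |
| 3 | 24.2 Gy | 34.9 Gy |
| 5 | 30.2 Gy | 41.3 Gy |
| 10 | 40.3 Gy | 50.2 Gy |
| 20 | 52.5 Gy | 58.4 Gy |

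**4. How many patients might change group?** The documents give no treatment mix, so this is an illustration only. Assume 29 evaluable patients, of whom k have one hypofractionated schedule and the rest are spread evenly from 50.4 to 77.4 Gy at 1.8 Gy per fraction. The table counts patients above the median on one scale but not on the other, at α/β 2, 3, 4 and 10.

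| Assumed schedule | k = 1 | k = 3 | k = 6 |
|---|---|---|---|
| 24 Gy × 1 | 2, 2, 2, 2 | 6, 6, 6, 6 | 12, 12, 12, 12 |
| 18 Gy × 1 | 2, 2, 2, 0 | 6, 6, 6, 0 | 12, 12, 12, 0 |
| 35 Gy in 5 | 2, 2, 2, 0 | 6, 6, 6, 0 | 12, 12, 5, 0 |
| 24 Gy in 3 | 0, 0, 0, 0 | 0, 0, 0, 0 | 2, 0, 0, 0 |

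Counts can exceed k because each patient who moves up pushes a conventional patient below the median. With any of the four schedules from 6.3.1.1 as the hypofractionated course, the count is 0 throughout.

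**The case against.** The strongest reply is that Gray is the protocol's own unit for treatment dose. Biologic equivalence defines only the minimum; above it, the recommended doses and the tissue limits are in Gray or GyRBE. A reader might infer that the SAP contradicts the protocol, but the documents do not support that. This part of the reply stands.

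The effect is also hypothetical. Every non-zero count in step 4 needs a schedule, a number of patients, a mix and an α/β that the documents do not supply. Stereotactic body radiotherapy gets one sentence and no dose. This stands too, and it is why the point is optional.

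The information is partly available already. Dose, fractions and radiation type are summarized by lesion, and all exposure data are listed by subject, so a reader could derive BED. The planned plots by therapy type do not fill the gap, because they separate only proton from other therapy. The SAP Introduction requires any analysis added later to be labelled as additional and unplanned, a modest cost for a descriptive display.

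Finally, BED brings its own assumption. With 18 Gy × 1 and k = 6, 12 of 29 patients change group at α/β 2 to 4 and none at 10. That is a real limitation, and the reason for a sensitivity value.

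**Conclusion.** The point holds as an optional improvement. A median cut in Gray does not measure radiation intensity once fraction size varies, and the plan allows it to vary. Whether this matters depends on a treatment mix that the documents do not give. The effect is nil for the full courses they name, and under the assumed mixes it ranges from 0 to 12 of 29 patients. All BED figures rest on the linear-quadratic model and an assumed α/β.

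Three stronger readings are tempting and are not supported:

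- **That patients in this trial are misgrouped.** Nothing in the documents shows that any patient receives a course that would change group.
- **That only stereotactic courses of a few very large fractions could matter.** Step 3 shows break-even at 10 fractions of 4.0 to 5.0 Gy and at 20 fractions of 2.6 to 2.9 Gy.
- **That the efficacy conclusion is at risk.** Only the descriptive percent-change plots and the exploratory PFS-ratio summaries and figures use these groups. Eligibility, the evaluable set and the rule of 4 responses in 29 do not.

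**What to change.** Before database lock, in SAP 3.5.3.3.1 and 3.5.3.4.1, define the dose groups as at or below versus above the median BED (or EQD2), or add this grouping beside the Gray split.

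- Derive it from the recorded total dose and number of fractions.
- Keep the SAP's per-subject rule by taking the highest BED among the subject's irradiated target lesions, and state the rule in both sections.
- Prespecify one α/β and one sensitivity value, chosen by the sponsor's radiation oncologists.
- State whether proton doses enter as physical or RBE-weighted dose.

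A split by fraction size alone, for example at 3 Gy, is not a good substitute. It would put 8 Gy × 1 with 24 Gy × 1 (BED 40 and 312 at α/β 2) and so recreate the mixing.

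The cost is one derived variable and a repeat of existing displays, since dose and number of fractions are already to be summarized. The downside is that the grouping then depends on the linear-quadratic model and an assumed α/β. Protocol 6.3.1.1 needs no change.
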